**1) IF NOT TAKING ANY BLOOD PRESSURE MEDICINES:**

- It looks like you are not taking any medicines for blood pressure, and it's high. As you learned from the video, it's very common to get high blood pressure as we get older.
- Have you ever been told your pressure is high before? *If this is the first time the pressure is high, suggest they get it rechecked at the pharmacy over the next week. Check back at the next session.*

*If they have been told the pressure was high in the past, suggest they talk to the doctor about it. Go to page 20 in the Client Plan Book and help client come up with a plan on how to reach out to the doctor: who is calling the doctor, when they are calling, what the client will say, potential barrier for carrying out the plan, and how they will get around the barrier. Write down plan in the Client Plan Book and check back at the next session.*

*When finished, go to **ACTIVITY 3 on page 54 of your manual.***

**2) IF ON MEDICINES BUT NOT TAKING CORRECTLY:**

*If they are missing doses because of side effects or cost, be supportive and tell them this happens to a lot of people.*

*Go to page 20 in the Client Plan Book and help client come up with plan on how to reach out to the doctor: who is calling the doctor, when they are calling, what they will say, potential barrier to the plan, and how to get around the barrier. Write down the plan in the Client Plan Book and check back at the next session.*

*If they are not having issues with side effects or cost but still not taking it correctly, supportively correct any mistakes. Tell them a lot of people find this confusing.*

*Go to page 21 in the Client Plan Book and help client make a plan for how to take correctly. Ask client to get their blood pressure rechecked after about a week, possibly at the pharmacist or at the doctor's office with the nurse. Write down the plan in the Client Plan Book and check back at the next session.*

- OK, let's see how that goes. I look forward to hearing about whether the blood pressure is better now that you are taking it like the doctor prescribed.

*Note: here are some common mistakes:*

- ✓ *Twice daily means morning and evening (not 2 doses in the morning)*
- ✓ *Many people skip doses of water pills if they are going out. If they do this, make sure they take it when they come back – don't skip a whole day.*
- ✓ *Some people only take them every other day.*

*When finished, go to **ACTIVITY 3 on page 54 of your manual.***

### 3) IF ON MEDICINES AND THEY ARE TAKING CORRECTLY:

It looks like you are taking the medicines just like the doctor prescribed, but the medicine may not be enough. What would you like to do about your blood pressure to get it under control? *Listen to what they would like to do. If they don't know what to do, suggest they talk to the doctor. If they agree to talk to the doctor, go to page 22 in the Client Plan Book and help client come up with plan on how to reach out to the doctor. Decide:*

1. *Who is calling the doctor, and when*
2. *What the client will say to the doctor*
3. *Whether the client needs a friend or family member with them to make sure their questions get answered; if yes, then who*
4. *Possible barriers to the plan, and what client will do to go around barriers*

*Check back at the next session.*

*Note: About 1 in 5 people may need 4 or even 5 blood pressure medicines to get the blood pressure below 140/90, and some can't get it down below 140/90. However, if the blood pressure is a lot lower than it used to be, that means the medicine is helping a lot and they are lowering risks, so you can praise them for getting it down, even if it's not below 140/90.*

*When finished, go to ACTIVITY 3 on page 54 of your manual.*

### Activity 3: How is My Cholesterol? -----

- OK, let's make sure that your cholesterol is where it needs to be.
- From your report card that you got at the start of the study, I see that your LDL cholesterol, or the "bad" cholesterol, was... *read out loud the LDL cholesterol number from page 2 in the Client Plan Book.*
- OK, if you don't mind, on page 16 of your Activity Book, write in your cholesterol number into the box at the bottom left-hand corner of the page.
- Can you tell me what this number means? Is it OK or is it high? *Let the client answer. If needed, remind client that less than 100 is the goal, whereas 100 or higher is high.*

*If the LDL cholesterol is less than 100, say:*

- Your cholesterol is in a great range. Congratulations! Now, we can review your homework from last week. Please turn to page 13 in your Activity Book.

***Go to Review of Last Week's Homework on page 57 of your manual.***

*If the LDL cholesterol is 100 or higher:*

- OK, so your cholesterol is high. Did you know that most people with diabetes have high cholesterol? So, you are not alone.
- If you and your doctor can get it under control, which is under 100, it will help you meet your goals and stay independent as long as possible.
- Let's go over your cholesterol medicines and make sure you are not having any problems. *Go to page 23 in the Client Plan Book to see if they're taking any medications for cholesterol.*

*If there are no cholesterol medicines listed, go to #1 on page 55 in your manual.*

*If there are cholesterol medicines listed, go over each medicine: how they're taking their medicine, whether they're experiencing side effects that are causing them to miss doses, and whether they're able to afford their medicine.*

- 1) If they are making mistakes in how they are taking it, or they are missing doses because of side effects or cost, go to #2 on page 56 in your manual.*
- 2) If they are taking it correctly and aren't missing doses because of side effects or cost, go to #3 on page 56 in your manual.*

### **1) IF NOT TAKING ANY CHOLESTEROL MEDICINES:**

- It looks like you are not taking any medicines for cholesterol and it's high. As I already told you, it's very common for people with diabetes to have high cholesterol. The two sort of go hand in hand.
- Have you ever been told your cholesterol is high before? *Listen supportively.*

*Note: Some people may have tried a medicine and it didn't agree with them, or they could not afford it, or they just didn't feel like taking it.*

*If your client mentions any of these things, discuss what they learned about cholesterol on the video.*

*Tell them about others in the community just like them who used to feel the way they do, but who now take cholesterol medicine.*

*Remind them that most people feel normal when on cholesterol medicine.*

*If they seem open to it, suggest making a plan to reach out to their doctor. Go to page 24 in the Client Plan Book and help client come up with a plan: who is calling the doctor, when they are calling, what the client will say, potential barrier for carrying out the plan, and how they will get around the barrier. Write down the plan in the Client Plan Book and check back at the next session.*

*When finished, go to Review of Last Week's Homework on page 57 of your manual.*

## 2) **IF ON MEDICINE BUT NOT TAKING CORRECTLY:**

*If they are missing doses because of side effects or cost, be supportive and tell them this happens to a lot of people.*

*Go to page 24 in the Client Plan Book and help client come up with plan on how to reach out to the doctor: who is calling the doctor, when they are calling, what they will say, potential barrier to the plan, and how to get around the barrier. Write down the plan in the Client Plan Book and check back at the next session.*

*If they are not having issues with side effects or cost but still not taking it correctly, supportively correct any mistakes. Tell them a lot of people find this confusing.*

*Go to page 25 in the Client Plan Book and help client make a plan for taking it correctly. Ask client to get cholesterol rechecked at the doctor's office after about a month. They can wait until their next regularly scheduled visit, which may not be for several months. Write down the plan and check back at the next session.*

- OK, let's see how that goes. I look forward to hearing about how it went and whether you got any side effects now that you will be taking the medicine every day like the doctor prescribed. If you do, we'll make a plan for how to handle that. How does that sound? *Let the client answer.*

*When finished, go to Review of Last Week's Homework on page 57 of your manual.*

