3. During this visit, we will also make a list of all medications the participant is currently taking.
4. Provide participant with health report card

After the completion of the in-person data collection, the participant will be given the materials for the program. If the participant is in the control condition, they will be given a general health education DVD. Participants in the intervention condition will be matched with their peer advisor and given an activity book that they will use during their sessions with their peer advisors. All participants will receive their portable DVD player at the end of the data collection visit. Participants will receive a Health Report Card that provides their a1c, LDL-cholesterol, blood pressure, and weight data. If needed, participant in the intervention arm will receive a study phone.

Participants will be asked by the research staff at the in person data collection visit if they would like to use a study phone. Study phones will be taken back at the 2nd in-person study visit. Copies of the consent, in-person data collection form, and Health report card are included in Appendix F.

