You heard someone on the video talk about blood pressure medications. What did you think about that? *Listen to their response. Bring out that she didn't really understand how*

*important blood pressure medicines were until well after she experienced a complication. Emphasize that high blood pressure is very common in your communities, and that the consequences of not taking care of high blood pressure can be very serious.*

- There are some important numbers to remember. Do you remember the numbers that mean you have high blood pressure? *140 over 90 or higher is high blood pressure.*
- If you don't get it under control, meaning lower than 140 over 90, high blood pressure can lead to serious complications. Do you remember any of these complications? *Complications include stroke, heart attack, dialysis, blindness.*
- One of the important points made on the video is that because it has no symptoms, high blood pressure can be especially dangerous. You may feel OK right up until you have a stroke. It's the "silent killer."
- Sometimes it can feel like the doctor is experimenting because they often switch the medications and change the dose. But this isn't experimenting, right? Many blood pressure medicines work better in some people than others, so it may take a while to get it right.
- Just like for diabetes, there are many different medications available to treat high blood pressure, so you should be able to get on a medication that both controls your blood pressure and lets you feel well.
- Some people do get side effects. Do you remember what the advice was if you get a side effect? *Let them tell you. It should be "talk to the doctor." You shouldn't just stop.*
- Now, the video also talked about high cholesterol. We learned that high cholesterol causes health problems. Do you remember what those were? *Answer: stroke and heart attack.*
- OK, here's a trick question. Do you remember what symptoms high cholesterol causes? *Answer: no symptoms with high cholesterol.*
- What about the "bad cholesterol", do you remember what that was? *Answer: LDL cholesterol.* OK, do you remember the good number you want to be below? *Answer: 100.*
- The main medicine for high cholesterol is a statin. Do you remember how many people feel well and have no side effects on statins? *Answer: 3 of 4.*

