## 3) **IF ON MEDICINES AND THEY ARE TAKING CORRECTLY:**

- It looks like you are taking the medicines just like the doctor prescribed, but the medicine may not be enough. What would you like to do about your cholesterol to get it under control? *Listen to what they would like to do. If they don't know what to do, suggest they talk to the doctor. If they agree, go to page 26 in the Client Plan Book and help client come up with plan on how to reach out to the doctor. Decide:*

1. *Who is calling the doctor, and when*
2. *What the client will say to the doctor*
3. *Whether the client needs a friend or family member with them to make sure their questions get answered; if yes, then decide who will call with them.*
4. *Possible barriers to the plan, and what client will do to go around barriers*

*Check back at the next session.*

*Note: About 1 in 5 people may get muscle cramps on statin medicines. This can be controlled by reducing the dose, or taking it every other day. The doctor may suggest one of these strategies.*

*When finished, go to Review of Last Week's Homework on page 57 of your manual.*

**Review of Last Week's Homework** -----□

- OK, now let's go over your homework from last week.
- Can you turn to page 13 in your Activity Book? *Let client get to the page.*
- Were you able to complete the homework?

*Note: if the client has not done some of the homework 2 sessions in a row, talk about what is making it hard to monitor. Let them know that since this is a research project, the investigators may want to help the person to succeed. Let them know that someone from the research team will be in touch.*

- *Call the research team within 24 hours and let them know what is happening.*
- *UAB staff will brief you on the conversation and the plan so that you can reinforce it next week.*

Client has not done homework for 2 sessions in row	2. Community coordinator calls back with next steps:
1. Community coordinator notified (note date / time):	

 
   
 
 date time 
	

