### Homework #4: High Blood Pressure Plan (Continued – page 2)

- ***If there were issues other than side effects or cost, and their plan to overcome the problem did not work:***
  - *Be encouraging and help them set a new plan for overcoming the problem. Write the new plan in the Client Plan Book and let client know you'll check back with them.*
- ***If there were issues other than side effects or cost, and their plan to overcome the problem worked:***
  - *Praise them! Ask them if they got their blood pressure rechecked. If not, encourage them to do so.*
  - *Make sure they aren't having any other problems with taking their blood pressure medication, and tell client you'll check back with them to see how they're doing.*

Notes:

- ***If they were not able to talk with the doctor about having high blood pressure even though they were taking their medication correctly:***
  - *Be encouraging and help them set a new plan for reaching out to the doctor. Write the new plan in the Client Plan Book and let client know you'll check back with them.*
- ***If they were able to talk with the doctor about having high blood pressure even though they were taking their medication correctly:***
  - *Praise them! Ask how it went and what the client and the doctor decided to do. Tell client you'll check back to see how they're doing with this the next time you talk.*

Notes:

**Homework #5: High Cholesterol Plan (only if client is on cholesterol medicine or should talk to doctor about starting treatment)**

- OK, let's discuss the plan we made last week for your high cholesterol.
- Last week, you wanted to... [go to Client Plan Book and read out loud the cholesterol plan that they chose to work on last week].
- Now, how did it go?

- ***If they were not on cholesterol medication and were not able to talk with doctor about starting medication:***
  - *Be encouraging and help them set a new plan for reaching out to the doctor. Write the new plan in the Client Plan Book and let client know you'll check back with them.*
- ***If they were not on cholesterol medication and were able to talk with doctor about starting medication:***
  - *Ask how it went and what the client and the doctor decided to do.*
  - *If client has decided to take cholesterol medication, be supportive and ask them if they have any questions about their new medication. Tell client you'll check back to see how they're doing.*

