### Homework #4: High Cholesterol Plan (Continued – page 2)

- ***If there were issues other than side effects or cost, and their plan to overcome the problem did not work:***
  - *Be encouraging and help them set a new plan for overcoming the problem. Write the new plan in the Client Plan Book and let client know you'll check back with them.*
- ***If there were issues other than side effects or cost, and their plan to overcome the problem worked:***
  - *Praise them! Ask them to get their LDL cholesterol rechecked after a month, if possible. They can wait until their next regularly scheduled appointment.*
  - *Make sure they aren't having any other problems with taking their cholesterol medication, and tell client you'll check back with them to see how they're doing.*

Notes:

- ***If they were not able to talk with the doctor about having high cholesterol even though they were taking their medication correctly:***
  - *Be encouraging and help them set a new plan for reaching out to the doctor. Write the new plan in the Client Plan Book and let client know you'll check back with them.*
- ***If they were able to talk with the doctor about having high cholesterol even though they were taking their medication correctly:***
  - *Praise them! Ask how it went and what the client and the doctor decided to do. Tell client you'll check back to see how they're doing with this the next time you talk.*

Notes:

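### The week-5 coaching script corrects how a blood pressure or cholesterol medicine is taken without first asking whether the doctor has changed it since the baseline visit

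*Combined protocol and SAP*

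**What the plan says.** **The list.** Under In-Person Biometric Data Collection Visit, the protocol states that "we will also make a list of all medications the participant is currently taking". Secondary Outcomes describes recording the name and dose of diabetes, blood pressure and lipid medicines at baseline and at follow-up. The pages available describe no update in between.

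**Week 5.** In the Peer Advisor Manual, Activity 2 goes on to medicines for clients whose baseline blood pressure was 140/90 or higher, and Activity 3 for those whose baseline LDL was 100 or higher. The coach opens the listed medicines in the Client Plan Book and covers three topics for each: how it is taken, whether side effects cause missed doses, and whether it is affordable. Each activity then has three branches. In branch 2 (on medicine but not taking it correctly), side effects or cost lead to a plan to contact the doctor. Otherwise both activities say: "If they are not having issues with side effects or cost but still not taking it correctly, supportively correct any mistakes". The coach then helps the client plan how to take the medicine correctly.

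**Changes are expected.** The DVD review in the same session says of doctors treating blood pressure that "they often switch the medications and change the dose". The note on statin cramps in Activity 3, branch 3, reads: "This can be controlled by reducing the dose, or taking it every other day. The doctor may suggest one of these strategies".

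**Two wordings.** The cholesterol branch looks ahead to side effects "now that you will be taking the medicine every day like the doctor prescribed". The blood pressure branch includes among its common mistakes: "Some people only take them every other day".

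**The concern.** A lay coach who corrects medicine-taking needs to know the current prescription. If the only written reference is a list made some weeks earlier, a schedule that the doctor has since changed can look like an error.

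An example built from the manual's own text: a client listed on a daily statin gets cramps and is moved by the doctor to alternate days before week 5. At the call the client reports alternate-day use and no current side effect. The side-effect route to the doctor no longer applies, so the branch leads to correction and a plan for daily use. A blood pressure dose that the doctor had lowered could be handled in the same way. The stake is a participant's safety and comfort on a changed regimen.

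**Working it through.** The plan gives no figure to reproduce. The check is a reading of the script plus arithmetic on session spacing.

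1. **Age of the list at week 5.** Sessions 1 to 5 contain four intervals, and the manual allows 7 to 10 days for each.
   - Session 1 to session 5: 4 × 7 = 28 days to 4 × 10 = 40 days.
   - The baseline visit precedes session 1, so the list is at least 28 days old.
   - The manual aims for session 1 within 7 days of the coach receiving the client's name. If the name arrives on the visit day, the upper end is about 40 + 7 = 47 days.

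2. **Which branches correct.** There are 3 blood pressure and 3 cholesterol branches, 6 in all. Branch 1 (no medicine) and branch 3 (taking correctly) do not correct. That leaves 2 of 6.

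3. **Do those two ask about a change?** The lead-in steps cover use, side effects and cost. Neither the lead-ins nor the two branches ask whether the doctor has altered the drug, dose or schedule: 0 of 2.

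4. **What is the test of correctness?** Week 5 does not define it. Week 1, Activity 1a, does so for diabetes medicines: the coach compares the client's account with the dose and frequency that staff entered in the Client Plan Book, and explains correct use if they differ. Carrying that practice over to week 5 is an inference. It rests on this step and on the baseline-and-follow-up recording described under Secondary Outcomes.

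5. **Does the manual ask elsewhere?** The week-4 A1c table, in the 8–9 row, makes its advice depend on whether medicines have changed since the A1c was measured. That applies to A1c only.

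6. **Follow-up in week 6, 7 to 10 days later.** For plans on issues other than side effects or cost there are four outcomes: worked or did not work, for each of blood pressure and cholesterol. None of the 4 asks about a doctor's change. If the plan worked, the blood pressure text is "Praise them! Ask them if they got their blood pressure rechecked. If not, encourage them to do so" and the cholesterol text is "Praise them! Ask them to get their LDL cholesterol rechecked after a month, if possible". Both of these outcomes (2 of 4) also tell the coach to check for any other problems with taking the medicine. If the plan did not work, a new one is set.

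7. **Rechecks.** Blood pressure is rechecked after about a week. Cholesterol is rechecked after about a month, and this may wait several months for the next regular visit.

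**The case against.** The strongest reply is that the harm needs several things at once: a doctor's change within about 28 to 47 days, on a listed medicine, in a client above the baseline threshold, who does not mention it when asked how the medicine is taken or when told it is being taken wrongly. Both branches name the doctor's prescription as the standard. Before the branches, clients are invited to ask questions, and those the coach cannot answer go to the study doctors or the client's own doctor. Coaches are told in week 1 to say that they are not clinicians and that the program does not manage medication. Under Safety Assessments, symptoms are checked at contacts throughout the 12-week phase, so before week 5 as well as after, and reported to the participant's physician. The recruitment form in Appendix B lists special calls around doctor visits, which could reveal a change. All of this stands, and it makes the risk smaller.

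Three stronger readings are tempting but unsupported.

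- A reader might infer that coaches are told to hold clients to the baseline list. Week 5 does not say so, and the list may serve only to show which drugs to discuss.
- A reader might infer that the program has no check for changed prescriptions. The Client Plan Book pages behind these branches are not in the part available and could hold a prompt or an updated list.
- A reader might infer that the manual calls doctor-ordered alternate-day statin use a mistake. The list of mistakes belongs to the blood pressure branch, and the statin note appears separately in the cholesterol activity.

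What remains is that the script leaves disclosure to the client. Coaches are told to cover and check off all session content, so a scripted question is more dependable than judgement on the call.

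**Conclusion.** The gap is real but narrow. In the script shown, both week-5 branches that correct medicine-taking do so without asking about a change made by the doctor, at least 28 days after the only list described. A doctor-ordered schedule could therefore be coached away. The risk is probably small. Its frequency cannot be estimated, because the documents give no rate of regimen change; the branch counts describe the text and do not measure harm.

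The conclusion assumes that the week-5 pages carry the baseline list and that the Client Plan Book has no prompt of its own. If either is wrong, the point weakens or falls away. It has no bearing on the endpoints, sample size or analysis. It is an inexpensive improvement to the script.

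**What to change.** In branch 2 of Activities 2 and 3, add a question before any correction: *Has your doctor changed how you should take this medicine since the study visit?*

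- **Yes:** do not correct to the listed schedule. Note the change and have the client confirm it with the doctor or pharmacist.
- **Unsure:** have the client read the label on the current bottle, and coach to that. Use the existing doctor-contact plan (Client Plan Book pages 20 and 24) only if the label and the list disagree. The week-5 greeting asks only for the Activity Book, so the client may need to fetch the bottle.
- **No:** proceed as now.

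Make two wording edits. In the cholesterol branch, replace the daily-use phrase with *the way your doctor prescribed*. In the blood pressure branch, add *unless the doctor told them to* to the alternate-day example.

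The cost is about a minute of call time. Clients who report a change, or whose label and list disagree, wait until the doctor or pharmacist is reached. That wait may exceed one 7-to-10-day interval, since week 6 itself provides for clients who have not managed to speak to the doctor. The label step keeps clients who are merely unsure from losing adherence coaching meanwhile.
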